1.1.3 Abbreviations and Acronyms

| | |
|------------|----------------------------------------------------------------------------------------------------------|
| ADE | Adverse Device Effect |
| AE | Adverse Event |
| ALCOACCEA | Attributable, Legible, Contemporaneous, Original, Accurate, Complete, Consistent, Enduring and Available |
| [REDACTED] | [REDACTED] |
| ASADE | Anticipated Serious Adverse Device Effect |
| ATC | Anatomic Therapeutic Chemical |
| BCVA | Best Corrected Visual Acuity |
| CA | Competent Authority |
| CI | Confidence Interval |
| CIP | Clinical Investigational Plan |
| CIR | Clinical Investigation Report |
| [REDACTED] | [REDACTED] |
| CMP | Clinical Monitoring Plan |
| CNIL | Commission Nationale de l'Informatique et des Libertés |
| CRO | Contract Research Organisation |
| CSP | Code de la Santé Publique |
| DD | Device Deficiency |
| [REDACTED] | [REDACTED] |
| DED | Dry Eye Disease |
| DES | Dry Eye Syndrome |
| DMP | Data Management Plan |
| e-CRF | Electronic Case Report Form |
| EDC | Electronic Data Capture |
| EU | European Union |
| FAS | Full Analysis Set |
| FDA | Food and Drug Administration |
| GCP | Good Clinical Practice |
| GDPR | General Data Protection Regulation |
| GMP | Good Manufacturing Practice |
| IB | Investigator Brochure |
| ICF | Informed Consent Form |
| IEC | Independent Ethics Committee |
| IFU | Instructions for Use |
| IMD | Investigational Medical Device |
| IRB | Institutional Review Board |
| IRT | Interactive Response Technology |
| ITT | Intent-To-Treat |
| IWRS | Interactive Web Response System |
| KCS | Keratoconjunctivitis Sicca |
| LFU | Lacrimal Functional Unit |
| [REDACTED] | [REDACTED] |
| MAR | Missing At Random |

| | |
|------------|-----------------------------------------------|
| MDR | Medical Device Regulation |
| MedDRA | Medical Dictionary for Regulatory Activities |
| [REDACTED] | [REDACTED] |
| MMRM | Mixed Model for Repeated Measures |
| NA | Not Applicable |
| NRS | Numeric Rating Scale |
| OSDI | Ocular Surface Disease Index |
| PI | Principal Investigator |
| PP | Per Protocol |
| PT | Preferred Term |
| QoL | Quality of Life |
| Q1 | First Quartile |
| Q3 | Third Quartile |
| [REDACTED] | [REDACTED] |
| RM | Rescue Medication |
| RMP | Risk Management Plan |
| RMR | Risk Management Report |
| SADE | Serious Adverse Device Effect |
| SAE | Serious Adverse Event |
| SAP | Statistical Analysis Plan |
| SD | Standard Deviation |
| [REDACTED] | [REDACTED] |
| SDR | Source Data Review |
| SDV | Source Data Verification |
| SOC | System Organ Class |
| SUSAR | Suspected Unexpected Serious Adverse Reaction |
| TBUT | Tear Break Up Time |
| TEAE | Treatment Emergent Adverse Event |
| USADE | Unanticipated Serious Adverse Device Effect |
| VAS | Visual Analogue Scale |

1.3 PRINCIPAL INVESTIGATOR AND INVESTIGATION SITE(S)**1.3.1 Investigators Details**

The Sponsor will maintain an updated list of Principal Investigators (PIs), and investigation sites, separately from this CIP, throughout the duration of the clinical investigation. The definitive list will be provided with the Clinical Investigation Report (CIR).

Roles, responsibilities, and qualifications of investigators are detailed in the CIP.

2 IDENTIFICATION AND DESCRIPTION OF THE IMD

2.1 SUMMARY DESCRIPTION OF THE IMD AND ITS INTENDED PURPOSE

The patient will be trained for the correct instillation technique of IMD. The patient will be provided with an information on the informed consent form, on the labels on the IMD boxes and with some reminders about storage and administration in the patient diary.

Test device: T2769 (Thealoz® Total)

T2769 is a sterile, phosphate-free and pH neutral solution. It contains Trehalose, Sodium Hyaluronate (SH) and Naaga.

T2769 device is presented in the ABAK® III multi-dose bottle (10 mL).

As per Instructions for Use (IFU), T2769 is indicated for the treatment of moderate to severe dry eye syndrome.

[figure not shown]
[figure not shown]
Comparative device: Hylo Forte®

HYLO-FORTE® is a sterile, phosphate and preservative-free solution for ocular use containing sodium hyaluronate, citric acid anhydrous, sodium citrate and sorbitol. It is presented in a COMOD® multi-dose application system (10 mL).

HYLO-FORTE® is an eye drop for the intensive and therapeutic lubrication of the ocular surface in more severe and persistent dry eye sensation including treatment after surgical procedures.

2.2 DETAILS CONCERNING THE MANUFACTURER OF THE IMD

The legal manufacturer of T2769 according to the EU Medical Device Regulation (MDR) 2017/745 is Laboratoires THÉA.

[figure not shown]

2.4 PACKAGING AND LABELLING

2.4.1 Packaging

The IMD will be packaged by approved contractor in accordance with ISO 14155 current version and EU MDR 2017/745. The IMDs will be prepared according to the packaging list provided by the CRO responsible for biometry (see Section 6.1.2.1).

T2769 is packaged in a multidose white polyethylene ABAK® III system bottle. The dispenser is already used in several currently marketed eye drops. This innovative and patented device provides eye drops through a 0.2 µm filter, preventing any bacterial contamination of the solution without the use of any preservatives:

HYLO-FORTE® is presented in a COMOD® multi-dose application system (10 mL).

The complete treatment for one patient and for the complete investigation duration will be as following:

| Packaging | Run-in treatment: Hydrabak® | T2769 or Hylo Forte® | |
|-------------|--------------------------------|-------------------------------------------------------|--------------------------------------------------------|
| | | Visit #2 Period Visit #2 - D1 to Visit #3 - D15 | Visit #3 Period Visit #3 - D15 to Visit #4 - D36 |
| Primary (I) | 1 vial | 2 vials | 2 vials |
| Final | 1 cardboard box | 1 cardboard carton | 1 cardboard carton |

Each patient will receive 1 preservative-free multidose bottle of Hydrabak® during the run-in period and 4 preservative-free multidose bottles of the IMD during the clinical investigation.

Hydrabak® is supplied in the ABAK® multi-dose bottle. This innovative and patented device provides eye drops through a 0.2 µm filter, preventing any bacterial contamination of the solution without the use of any preservatives.

2.4.2 Labelling

All labels will be written in the local language. The content of the labelling is in accordance with ISO 14155 current version and EU MDR 2017/745 specifications and requirements.

Each vial of run-in treatment and IMD will carry one label.

The cardboard carton of IMD will also carry a detachable label (flag label) bearing at least the CIP number and IMD kit number. This label will be torn off by the person dispensing the IMD to the patient and will be stuck in the space provided in the IMD allocation form to record the dispensing procedure.

2.5 INTENDED PURPOSE OF THE IMD IN THE PROPOSED CLINICAL INVESTIGATION

T2769 is intended to hydrate and soothe itchy, red or irritated eyes in case of moderate to severe dry eye syndrome.

2.6 THE POPULATIONS AND INDICATIONS FOR WHICH THE IMD IS INTENDED

T2769 is indicated in moderate to severe dry eye syndrome.

T2769 is suitable for adults (patients over or equal than 18 years excluding pregnant or breastfeeding women, see Sections 6.3.1 and 6.3.2).

2.7 DESCRIPTION OF THE IMD

T2769 is an ophthalmic solution composed of trehalose (3%), sodium hyaluronate (0.15%), N-Acetyl Aspartyl Glutamic Acid Sodium salt (Naaga, 2.45%), [REDACTED]

The solution is supplied in the ABAK® III multi-dose bottle. This innovative and patented device provides eye drops through a 0.2 µm filter, preventing any bacterial contamination of the solution without the use of any preservatives.

The product can be used until 3 months after first opening.

Table 4 Investigational Medical Device T2769

| Names of ingredients | Percentage formula (g/100 ml) | Function | Reference to standards |
|------------------------------------------------------------------|-------------------------------|------------------------------|-------------------------|
| Trehalose dihydrate* | 3.00* | Lubricating, hydrating agent | Current Eur. Ph. [2297] |
| N-acetyl aspartyl glutamic acid, sodium salt (NAAGA, Na)* | 2.45* | Soothing agent | Internal monograph |
| Sodium hyaluronate** | 0.15* | Lubricating, hydrating agent | Current Eur. Ph. [1472] |

* The quantity of the ingredient (Trehalose dihydrate and Naaga Na) is adjusted as a function of its titre and water content

** The quantity of this ingredient is adjusted as a function of its water content

The excipients of the T2769 eye-drops [REDACTED] are well-known and commonly used in ophthalmic formulations.

Batch number and expiry dates will be provided in the certificate of analysis and will be specified on the packaging.

2.8 STORAGE CONDITIONS AND INDICATIONS OF USE

All IMD should be stored in its original packaging, protected from light and moisture, at a temperature between 8°C and 25°C and the expiry date refers to the last day of that month as long as the packaging is intact, and it has been stored correctly.

The IMD must not be used if the vial is damaged and must not be refrigerated or frozen.

Until dispensed to the patient, products should be kept in a secure area with restricted access. The investigator, the hospital pharmacist or other personnel allowed to store and dispense IMD(s) will be responsible for ensuring that the IMD(s) are securely maintained as specified by the Sponsor and in accordance with the applicable regulatory requirements.

The IMD should not be used after the expiry date indicated on the outer cardboard box. The expiry date refers to the intact correctly stored packaging.

The product can be used until 3 months after first opening.

If significant changes and/or update on labelling, handling and storage are required during the clinical investigation, the corresponding sections will be updated by notifying or submitting to Competent Authorities (CAs) concerned accordingly. All investigators' sites will be immediately informed about any change by the Sponsor. Investigator or a delegate will inform the patient, if any.

Accordingly, the Sponsor may decide to halt temporarily the recruitment (see Section 16.1). In any way, the reasons and the procedures for any changes will be justified and described by the Sponsor.

2.9 DESCRIPTION OF THE SPECIFIC MEDICAL OR SURGICAL PROCEDURES INVOLVED IN THE USE OF THE IMD

NA.

2.10 INVESTIGATOR BROCHURE (IB) AND INDICATION FOR USE (IFU)

All details concerning the IMD are specified in the IB and the IFU. These documents will be updated whenever necessary and all applicable versions will be provided to each investigation site throughout the clinical investigation.

At time of CIP writing, validated and applicable version are:

- For the IB: V4, MAR-2024,

- For the IFU: Ver. 9-07/2023.

2.11 DESCRIPTION OF COMPARATIVE DEVICE

[figure not shown]
Hylo Forte® is purchased from Scope Ophthalmics. It is a sterile, phosphate and preservative-free solution for ocular use.

[figure not shown]
[figure not shown]
Packaging and labelling are provided in Sections 2.1 and 2.4, batch number and expiry dates will be specified on the packaging.

[figure not shown]
Storage conditions are specified in Section 2.8.

One ml of HYLO-FORTE® contains 2 mg sodium hyaluronate, citric acid anhydrous, sodium citrate, sorbitol and water for injections.

[figure not shown]

3.4 DESCRIPTION OF THE CLINICAL DEVELOPMENT STAGE

The investigation is defined as a post-market stage (refer to ISO 14155:2020). The clinical investigation design is confirmatory.

4 BENEFITS AND RISKS OF THE IMD, CLINICAL PROCEDURE AND CLINICAL INVESTIGATION

4.1 ANTICIPATED CLINICAL BENEFITS

4.3 RISKS ASSOCIATED WITH PARTICIPATION IN THE CLINICAL INVESTIGATION

Laboratoires THÉA performed a risk analysis according to the current ISO 14971 standard.

[figure not shown]
All risks identified in Laboratoires THÉA's risk analysis were mitigated. The remaining residual risks were considered to be of negligible or acceptable levels. This is fully described in the Risk Management Report (RMR). The risks mitigated to this latter risk level (acceptable) are described in section **4.5**.

[figure not shown]
[figure not shown]
All the possible warnings have been put in place in the instructions for use as well as on the secondary and primary packaging if possible.

These hazards cannot arise in the normal conditions of use.

4.4 POSSIBLE INTERACTIONS WITH CONCOMITANT MEDICAL TREATMENTS

To avoid possible interactions with a concomitant treatment, patients will be asked to wait at least 15 minutes between use of the IMD and any other eye product.

5 OBJECTIVES AND HYPOTHESES OF THE CLINICAL INVESTIGATION

5.1 CLAIMS FOR CLINICAL PERFORMANCE, EFFECTIVENESS OR SAFETY OF THE IMD

There is no claim concerning the clinical performance of THEALOZ TOTAL in the IFU. However, the following clinical performances support the claimed clinical benefits:

- THEALOZ TOTAL reduces ocular surface damages.
- THEALOZ TOTAL increases tear film stability/quantity.

As per the IFU, the claim on clinical safety is:

- THEALOZ TOTAL is well tolerated on the ocular surface.

As per the IFU, the clinical benefits of THEALOZ TOTAL are:

- THEALOZ TOTAL relieves from the symptoms of dry eyes.
- THEALOZ TOTAL soothes the eyes from itchiness and irritation.
- THEALOZ TOTAL reduces the redness of the eyes.

As per Laboratoires THÉA, other clinical benefit of THEALOZ TOTAL is improvement of (global) ocular comfort.

[figure not shown]
5.2 OBJECTIVES, PRIMARY

The primary objective of the investigation is to demonstrate the non-inferiority of T2769 compared to Hylo-Forte® in terms of total ocular surface staining (Oxford score) in patients with moderate to severe DES.

5.3 SCIENTIFIC JUSTIFICATION AND CLINICAL RELEVANCE FOR EFFECT SIZES, NON-INFERIORITY MARGINS OR EQUIVALENCE LIMITS

Estimation of the standard deviation and determination of the non-inferiority limit are based upon data of previous studies and literature.

Concerning the non-inferiority limit, according to clinicians, a variation not exceeding 2 points in the total Oxford grade is considered as not clinically significant (Labetoulle et al. 2022; Chiambaretta et al. 2017; Baudouin et al. 2012).

5.5 RISKS AND ANTICIPATED ADVERSE DEVICE EFFECTS

There are no specific risks and ADE to be assessed during this clinical investigation.

6 DESIGN OF THE CLINICAL INVESTIGATION

6.1 GENERAL

6.1.1 Justification of the Investigation Design

Methodology: a 5-week, international, multicentre, randomised, investigator-masked, 2 parallel groups (T2769 versus Hylo-Forte®) investigation.

- Multicentre

The investigation will be performed in different sites in EU.

A multicentre (and multi-investigator) design will provide the possibility of recruiting the patients from a wider population than a single-centre design and of using the device in a broader range of clinical settings, thus presenting an experimental situation that is more typical of future use. In this case, the involvement of a number of investigators also gives the potential for a wider range of clinical judgments concerning the value of the therapeutic intervention. In addition, it is also a practical means of accruing sufficient patients to satisfy the investigation objective.

- Randomised

At the randomisation visit on Day 1, a patient fulfilling all eligible criteria will be randomly assigned to 1 of the 2 treatment groups (T2769 or Hylo-Forte®). Randomisation ensures the investigator remains masked to product assignment for DES treatment. It is generally considered the most reliable method for evaluating the effects of interventions.

- Choice of run-in period

Patients meeting the screening criteria will undergo a 7-10-days run-in period. During this period, all patients will substitute their current dry eye treatment with Hydrabak®, ophthalmic solution containing NaCl 0.9%. Patients will instill 1 drop in each eye, from 3 to 6 times daily.

[Redacted content block] (Baudouin et al. 2017; Chiambretta et al. 2017; Labetoulle et al. 2018; Holland et al. 2019).

- Investigator-masked

A double-masked investigation design is not possible due to different commercial packaging between T2769 – Hylo-Forte®.

However, the identity of the IMD given to each patient will not be known for the masked investigator who is independently in charge of the ophthalmic examination.

To this aim, the masked investigator will differ from the person who will record the used/unused IMDs. The recording will be delegated either to the hospital pharmacy or to a trained collaborator (trained by the masked investigator; hereafter referred to as unmasked collaborator). Therefore, the masked investigator should not receive the returned IMDs from the patients and returned IMD must be stored in a different place from the IMD that have not yet been dispensed. Patients will also be trained to not report any information that could lead to unblinding in the diary and to the masked investigator.

If the masked investigator become unmasked, then the patient continues the clinical investigation. The patient data will be handled accordingly for the analysis.

- Choice of the comparator group

[REDACTED]

- Choice of the investigation population

[REDACTED]

- Scheme of administration

The dose regimen recommended is 1 drop in each eye, from 3 to 6 times daily.

- Choice of the treatment period

A 5-week treatment period may allow to evaluate the therapeutic effect and to observe any potential safety issues.

A period of 1 month is usually the minimum time required to demonstrate the therapeutic effect of a product.

- Choice of primary endpoint

The primary [REDACTED] endpoint [REDACTED] of this clinical investigation (total ocular surface staining (Oxford scale), [REDACTED]

[REDACTED] (Jones et al. 2017; Aragona et al. 2019; Fariselli et al. 2018; Mateo Orobio et al. 2017; Nasser et al. 2018; Pinto-Bonilla et al. 2015; Chiambaretta et al. 2017; Novack et al., 2017; Wolffsohn et al., 2017; Begley et al., 2019; Nichols et al., 2021; Begley et al., 2022). Consequently, these endpoints are clinically relevant, clearly defined and assessed at specified time points in order to provide clinical evidence on the efficacy [REDACTED] of T2769 in its intended use (i.e., improvement of the ocular signs and symptoms in DED patients).

- Symptom assessment

Ocular symptoms (except symptoms immediately after drop instillation, not assessed at inclusion) as well as AEs will be assessed at all investigation visits.

6.1.2 Description of the Measures to be Taken to Minimize or Avoid Bias

6.1.2.1 Randomisation

The use of randomisation attempts to mitigate accidental bias (such as selection bias), promoting comparability of the study groups and serves as a basis for statistical inference for quantitative evaluation of the treatment effect.

The randomisation code list stratified by site and lists of IMDs kit numbers for the packaging is generated by the CRO responsible for biometry. Patients will be randomised on a 1:1 basis to T2769 or Hylo-Forte® respectively.

Randomisation list(s) and lists of IMD numbers for the packaging are to be kept securely by the editor according to their procedures.

The IMD packaging list is to be kept by the company responsible for manufacturing and labelling of the treatment kits.

The randomisation and the IMD kit number will be allocated to the patients according to randomisation list using an Interactive Response Technology (IRT).

Randomisation will occur at Randomisation Visit (Visit #2 - D1) after all procedures have been performed and eligibility for the clinical investigation confirmed. The patient who meets the eligibility criteria will be randomly assigned to treatment and associated to a randomisation number.

6.1.2.2 Concealment of Allocation

Concealment of allocation will be ensured using an IRT system to perform IMD kit number allocation so that it's not possible for the investigators to know the allocation sequence in advance.

6.1.2.3 Masking and Code Breaking

Serious biases may occur in a clinical investigation including investigator bias (which may arise due to knowledge by the investigator of treatment allocated to a particular patient), evaluator bias and placebo effects. To protect an investigation against these potential biases, masking will be used.

This will be an investigator-masked clinical investigation.

The **masked investigator** will remain masked to the IMD (T2769 – Hylo-Forte®). He/she will not receive the returned IMD from the patients.

The following-up and the number of returned IMDs will be recorded by **unmasked collaborator** throughout the clinical investigation.

The **unmasked collaborator** will also be in charge of incidents reporting as it may include information that could lead to unblinding.

Masking will be achieved by coding the interventions, providing each product unit with identical cardboard box and by identifying it by an IMD kit number.

The code should not be broken except:

- in case of medical emergency (where knowledge of the IMD received would affect the treatment of the emergency),
- or when it is a regulatory requirement (e.g., for serious incident).

The investigator is responsible for accessing the IRT System to obtain the name of the IMD received by the patient.

If an emergency code breaking becomes necessary, the investigator should notify the Sponsor.

When a code is broken, the date, time and reason must be recorded in the patient's Source and in any associated AE report. The identity of the IMD should not be disclosed in these documents.

The incident form must be completed by unmasked staff. Further to a serious incident assessment by the Global Drug Safety & Medical Information Department, the code might be broken for reporting purposes. The relevant Laboratoires THÉA, Contract Research Organization (CRO), masked investigator and masked staff remain unaware of the identification of the IMD as per the above-mentioned process.

The overall randomisation list will be broken for data analysis after database lock.

6.1.2.4 *Management of potential confounding factors*

NA

6.1.2.5 *Dispensing*

IMD will be dispensed by the masked collaborator and/or pharmacist or authorised person delegated by the investigator and according to the local regulations. Each dispensing of IMDs will be recorded in the appropriate documentation.

During the whole investigation treatment period, the **masked investigator and/or delegate** will remain masked to the IMD (T2769 – Hylo-Forte®). He/she will not receive the returned IMD from the patients.

All information regarding the use of the IMDs will be contained in the package given to patients.

The IMDs must be dispensed only to patients in accordance with the CIP and the randomisation.

As soon as the patient has signed the Informed Consent, he/she will receive a patient number in the Electronic Case Report Form (e-CRF).

Once all screening criteria have been checked, the patient will receive a box including Run-in Hydrabak® treatment for the run-in period.

At the randomisation visit (Visit #2 - D1), once inclusion and exclusion criteria have been checked and once the patient is eligible, the randomisation will be performed and the IRT will provide the IMD kit number allocated to the patient.

At the other visit (Visit #3 - D15) with dispensation, the IRT will provide the IMD kit number allocated to the patient.

Two dispensations will be performed as follows:

- At randomisation (Visit #2 - D1): one box containing enough bottles for the treatment period Day 1 to Day 15 ± 1 day will be provided by the investigator (or delegate) or pharmacist with the number assigned by the IRT.
- At Visit #3 - D15: one box containing enough bottles for the treatment period Day 15± 1 day to Day 36 ± 3 days will be provided by the investigator (or delegate) or pharmacist with the number assigned by the IRT.

The site team member will instruct patient on the method of instilling the doses and will train his / her patient to not disclose the IMD characteristics neither during the visit nor when reporting / discussing AE / Device Deficiency (DD). If the IMD is dispensed by a masked investigator, he must not open the IMD kit in order to avoid unblinding.

[REDACTED]

6.1.2.6 *Primary Performance Endpoint*

The primary performance endpoint is the change from baseline^a (D1) in total ocular surface staining grade according to Oxford 0-15 grading scheme^b at D36 in the study eye^c.

It is the most commonly used endpoint in clinical trials with DED patients. It is performed to detect ocular damage surface, which is considered as a hallmark sign of DED.

As per literature, 1 month is a standard approach, commonly considered enough to assess a product performance in dry eye. In addition, in the previous clinical investigation on T2769 conducted by Laboratoires THÉA (CIR LT2769-001/17E1044), the improvement was rapidly observed after 14 days of treatment (see Section 3.3).

[figure not shown]
Thus, the change from baseline (D1) in total ocular surface staining grade according to Oxford 0-15 grading scheme^b (corneal staining by fluorescein and conjunctival staining by fluorescein with a yellow filter at D36 in the study eye^c) was set as the primary performance endpoint to evaluate the performance of the treatment.

Different ocular surface staining scales have been developed and despite common usage, a universally accepted “gold standard” grading scale does not exist for corneal and conjunctival staining. This investigation will use the Oxford scale, a widely used and standardised grading scale. International regulatory agencies such as the Food and Drug Administration (FDA) rely on corneal and conjunctival staining measurement as a primary endpoint in clinical trials of commercially registered dry eye treatments (Begley et al. 2019).

^abaseline is defined as the assessment at randomisation visit before the first IMD instillation. Missing value at randomisation visit will not be replaced.

^bthe analysis will be performed following original oxford scale [REDACTED]

[figure not shown]
[figure not shown]
^cdefined in the statistical considerations section (see Section 7.2).

6.1.2.8 *Safety Endpoints*

The following safety [REDACTED] endpoints will be assessed:

- Treatment-Emergent Adverse Events (TEAEs) by System Organ Class and Preferred Term (separately for ocular and systemic TEAE).

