6.1.5.2 *Treatment Period*

Visit#2: Randomisation Visit (Day 1)

Visit#2 will consist of the following procedures and examinations by the investigator or authorised delegate who will perform the ophthalmologic examination during all the visits and according to the following order in each eye.

By the masked investigator or authorised delegate, the same as the screening visit (according to local requirements, the investigator may delegate tasks to collaborator).

- Questioning about previous and concomitant ocular and non-ocular treatments
- OSDI Questionnaire
- DEAL questionnaire
- Ocular discomfort (VAS)
- Questioning about dry eye related ocular symptoms within the last 48 hours
- Measurement of Far BCVA*
- Tear Sampling for IL6 and IL8 concentration assessment**
- Slit lamp examination* for measuring:
 - Measurement of conjunctival hyperaemia* [REDACTED]
 - [REDACTED] Oxford 0-15 grading scheme* (corneal staining by fluorescein and conjunctival staining by fluorescein with yellow filter),
 - TBUT*
- Schirmer test* (without anaesthesia)
- AE reporting
- Verification of inclusion and exclusion criteria
- Randomisation (IRT system)
- IMD dispensation
- Questioning about Run-in treatment compliance
- Check of the patient diary completion with the patient
- Status of the patient (Screen failure or randomised)

By the unmasked collaborator:

- Incidents reporting

The next visit must be scheduled 15 days after Visit #2 (± 1 day) at the same hour (± 2 hours).

Site staff must remind the patients:

- how to complete the patient diary,
- to not report any information that could lead to unblinding in the diary,
- to not report any information that could lead to unblinding to the masked investigator,
- to bring the patient diary back at Visit #3,
- how to instil IMD and to respect posology of 1 drop in each eye, from 3 to 6 times daily,
- that no IMD must be instilled for at least 2 hours before Visit#3.

*Ophthalmological examinations and assessments MUST be performed by the SAME masked investigator for all the visits and using the same slit lamp.

**It's necessary to wait at least 15 minutes after tear sampling to perform the next ophthalmic assessment.

Visit#3: Day 15 (\pm 1 day)

Visit#3 will consist of the following procedures and examinations by the investigator or authorised delegate who will perform the ophthalmologic examination during all the visits and according to the following order in each eye.

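### Masked staff, including the examiner who grades the primary endpoint, may dispense the product in a closed kit, and the visible text then assigns nobody to show the patient the allocated bottle

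*Protocol*

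**What the plan says.** Protocol 6.1.1 says double masking is impossible because the two products differ in commercial packaging, so the trial relies on a masked examiner. Under 6.1.5.2 the same masked investigator must do every ophthalmological assessment at every visit. That includes the Oxford staining grade, which is the primary endpoint.

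On who hands over the product, 6.1.2.5 states: "IMD will be dispensed by the masked collaborator and/or pharmacist or authorised person delegated by the investigator". It then has the D1 and D15 boxes provided by the investigator, a delegate or a pharmacist, and it foresees the masked case directly: "If the IMD is dispensed by a masked investigator, he must not open the IMD kit in order to avoid unblinding".

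On instruction, the sentence just before that rule reads: "The site team member will instruct patient on the method of instilling the doses". Section 2.1 requires that "The patient will be trained for the correct instillation technique of IMD". The Visit 2 reminders from site staff include "how to instil IMD and to respect posology of 1 drop in each eye", and Visit 3 has a matching reminder.

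On containers, T2769 comes in ABAK III (2.1) and Hylo-Forte in COMOD (2.4.1). For the run-in, which every patient takes for 7 to 10 days, 2.4.1 says "Hydrabak® is supplied in the ABAK® multi-dose bottle".

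**The concern.** The outer boxes are identical, so the mask is safe only while the box stays shut in the examiner's presence. A person who must keep it shut cannot show the patient the bottle inside. If that person is the examiner, ordinary patient behaviour, such as opening the box or asking how the bottle works, can reveal the arm. The exposure arises at D1 and D15, so it comes before both post-baseline gradings (D15 and D36).

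Two things are at stake. The first is the masking of a visual grade, which 6.1.2.3 says is there to guard against investigator and evaluator bias. The second is correct use of the comparator. In a non-inferiority trial, poorer use of the comparator makes the test product easier to pass.

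**Working it through.** The point is procedural and the plan has no figure to reproduce, so the check is to read the provisions together.

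1. **Who may dispense.** The opening of 6.1.2.5 names a masked collaborator, a pharmacist or an authorised delegate. Its dispensing schedule names the investigator, a delegate or a pharmacist. The Visit 2 and Visit 3 lists in 6.1.5.2 place dispensing under the masked investigator or authorised delegate. The unmasked collaborator's list has only incident reporting at Visit 2, and returns plus incident reporting at Visit 3. No visible provision gives dispensing to the unmasked collaborator by name.

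2. **Is masked collaborator a slip?** It may be. Section 14.5 gives the incident form to the unmasked collaborator in one paragraph and to the masked collaborator in the next. Section 14.6, however, names both roles in one sentence as if they were different people. Correcting the word would not settle the matter, because the closed-kit rule and the visit lists still allow masked dispensing.

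3. **Who instructs.** Sections 2.1, 6.1.2.5 and 6.1.5.2 all require instruction or reminders. The instructor is a site team member or site staff, with no mask status stated. Nothing visible says how the allocated container is shown when the kit stays closed.

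4. **Is the gap even between arms?** Run-in is ABAK for everyone. T2769 patients then move to ABAK III and Hylo-Forte patients to COMOD. A shared product-family name suggests some familiarity in the T2769 arm, but the documents do not say that ABAK and ABAK III handle alike.

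5. **Direction of a handling effect.** Section 7.2.1 defines the difference as D = mean change on T2769 − mean change on Hylo-Forte. It concludes non-inferiority if the upper bound of the two-sided 95% CI is no higher than +2. A higher Oxford score means more staining. Suppose poorer handling costs the Hylo-Forte arm an average of δ > 0 points of improvement. Its mean change then rises by δ, D falls by δ, and the upper bound moves δ further below +2. That favours non-inferiority. δ would be the share of patients affected times the loss per affected patient, and the documents give neither.

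6. **Direction of an unmasking effect.** An examiner who learns the arm could lean either way. No sign can be given.

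**The case against.** The strongest reply is that the protocol already provides safe routes. A pharmacist or authorised delegate may dispense, and nothing visible stops an unmasked one from opening the kit and teaching the patient. All use information is in the package (6.1.2.5). Section 2.1 adds information in the consent form, on box labels and in the diary. Patients are trained not to reveal the product, and the masked investigator never takes returned product. Instillation technique, one drop into the lower conjunctival sac, can be taught without the bottle. These safeguards are real and they limit the risk. They do not make the safe route mandatory, and they do not say who shows the bottle when a masked person dispenses.

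A reader might infer four stronger things that the documents do not support:

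- **Either the mask is broken or the training fails.** A pharmacist or unmasked delegate avoids both. A masked dispenser may also give general instruction and rely on the package information.
- **Only the comparator arm suffers.** The closed-kit rule applies to both arms. All patients have already used artificial tears in unspecified containers, and equal handling of ABAK and ABAK III is not stated.
- **Used bottles are present during grading because returns are listed after the examination.** The lists are grouped by person, and their order does not fix the sequence between examiner and collaborator. The documents are simply silent on when bottles change hands.
- **A bias in Oxford points can be quoted.** Any such figure would rest on an invented share affected and an invented loss per patient.

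A redacted block follows shortly after the closed-kit rule within 6.1.2.5 and may hold further dispensing rules. If so, the visible provisions would still need to be reconciled with it.

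**Conclusion.** The point holds as a gap in role assignment. As visible, the protocol lets masked staff dispense, including the examiner who grades the primary endpoint, while leaving container-specific instruction unassigned in that case. This puts the mask at avoidable risk. It also makes a handling disadvantage for Hylo-Forte plausible, and such a disadvantage would favour a non-inferiority conclusion.

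No size can be given. The arm-specific reading assumes that run-in practice with ABAK carries over to ABAK III. The overall reading assumes that the redacted text does not already assign these tasks. Confidence is therefore moderate. The correction is still worth making, because the primary endpoint is a subjective grade and the change is cheap.

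**What to change.** - **Section 6.1.2.5:** replace masked collaborator with unmasked collaborator, and remove the option for the masked examiner to dispense. State that the pharmacist or unmasked collaborator, as local regulations allow, dispenses and gives container-specific instruction at D1 and D15, after the masked examination and out of the examiner's sight.
- **Section 6.1.5.2, Visits 2 and 3:** move dispensing and the instillation reminders to that person's list.
- **Section 6.1.5.2, Visits 3 and 4:** state that returned bottles go to that person before the patient sees the examiner. This settles a point on which the text is silent.

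The unmasked collaborator or pharmacist already has tasks under 6.1.1, 6.1.2.3 and 11.1, so no new role is created. The cost is protocol wording, a few more minutes of existing unmasked staff time per visit, and a check of local dispensing rules, since 6.1.2.5 makes dispensing subject to them. Opening kits on site is a new exposure, which is why the instruction must take place away from the examiner.
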